3.6 Assessment of End-Points

Please see the glossary at the start of this protocol for definitions

Co-Primary End-Points

(i) Number of school days missed among those eligible to be in school.

Daily school attendances will be obtained from the school register and absences recorded with reconciliation with COVID-19 associated absences. This will be compared between study arms, to historic schools' data, and to national schools' benchmark data collected via a survey of non-participating schools.

(ii) Estimated number of in-school COVID-19 transmission events

The number of positive cases will be obtained from the following sources:

- 1. Weekly LFD active case finding (Control and Intervention Arms)
- 2. Symptomatic individuals' NHS Test and Trace results obtained from Community Testing routine data (Control and Intervention Arms)
- 3. In-school LFD DCT testing (Interventional Arm).

Positivity rates will be reported for each source separately to facilitate like-for-like comparison between arms

Epidemiological links between cases will be obtained from the NHS Test & Trace Contact Tracing and Advice Service data base. Additional links will be obtained by membership of school-reported contact groups. Onward transmission from the index case will be determined by the following:

• Genomic sequence of virus: The additional PCR swab collected from positive individuals will be used to determine the whole genomic sequence of isolates. A sample of apparent links will be assessed with comparisons of whole genome sequencing. The diversity of genetic sequences both in the schools and the

community (routinely determined by COG) will be used to help interpret the results. Preliminary work currently undertaken will determine the appropriate genetic distance to be used to exclude a direct transmission event between individuals. This is likely to be 2 SNPs.

- Plausible epidemiological link (e.g. membership of same close contact group)
- For positive individuals identified in DCT the DMIC will review all available data to determine if the individual's infection was likely to have resulted from onward transmission from the index case, or via co-infection from an unknown 'upstream' positive or out-of-school positive case.

Secondary End-Points

(iii) Number of positive first-order contacts missed by daily LFD testing (Intervention arm only).

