The number of Covid-19-associated missed days at school is dependent on the number of positive cases identified and the number of contacts of these cases that are self-isolating. Each positive case is self-isolated for 10 days. In the control group all first order contacts will also be self-isolated for 10 days. It is expected that this trial will occur in the summer term when the number of cases in a school will be low. For instance, it is expected that in the control group about 30% of children (and their parents) will consent to participate in regular weekly active case finding testing. For the purposes of the power calculation, it is assumed that the expected number of index cases identified is about 1 outbreak/month. Each index cases will lead to identification of 50 children in their bubble who will need to self-isolate each for 10 days. The number of index cases identified is a Poisson distribution with mean 1/month with each index cases leading to 510 missed school days.

In the intervention group, it is expected that a more complex set of interactions will occur. The ability to avoid self-isolation by DCT is likely to make participation in weekly active case finding testing more

⁸ Quartagrio et al, 'Handling an uncertain control group event risk in non-inferiority trials: non-inferiority frontiers and the power-stabilising transformation' (2020)

attractive with an increase in consent to voluntary weekly active case finding testing to 60%. This in turn will lead to the identification of more positive cases with initially an expected number of 2 different index cases identified per week. However, it is expected that 70% of children will volunteer for DCT and therefore only 15 children (25% of 50) will self-isolate. In addition, about 2 contacts will be identified by LFD testing as positive during DCT (5% of 35). It is expected that these 2 children will only have contacts within the bubble and therefore they will not lead to identification of more children. In all, each index cases will lead to the index cases or 360 missed schools / month

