In addition, the intervention will lead, over time, to a decrease in transmission and therefore detection of cases through an increased identification and isolation of true positives, itself arising from an increase of uptake of weekly active case finding testing. However, this decrease will be offset by the possible increase in in-school transmission by infectious children not undertaking DCT who attend school.

It is expected that the trial will start in the Summer term with 100 schools enrolled into each arm. However, it is likely that only 50% of enrolled schools will manage to sustain the trial leaving only 50 schools in each group.

	Control Group	Intervention Group
Number of schools successfully participating	50	50
Proportion of children consenting to mass testing	30%	40-60%
Initial number of outbreaks detected/school	1/month	2/month
Number self-isolating (incl. index case and) each for 10 days	51	10-30
Number of schools in each arm	50	50

*Including index case and 2 cases in each DCT bubble of 50 children test positive and therefore need 10 days of self-isolation

Table 1: Assumptions in Power calculation

The number of schools required in each arm to determine whether school attendance has been increased by the intervention will depend on the number of children volunteering for DCT and the increase in the proportion of children consenting for weekly active case finding testing.

Assuming that 30% of the control arm participate in weekly active case finding testing, the number of schools per arm for a two month study is shown in the following table (power of 80%, two-sided alpha (0.05))

Number (per index case) in intervention group	Proportion if children consenting to weekly active case finding testing in intervention arm		
self-isolating and not undertaking DCT	40%	50%	60%
7	10	12	14
8	11	13	15

911141810121521111317241214192913152236141826451518305816203579172343112182653170192967172033871172138117				
11 13 17 24 12 14 19 29 13 15 22 36 14 18 26 45 15 18 30 58 16 20 35 79 17 23 43 112 18 26 53 170 19 29 67	9	11	14	18
12 14 19 29 13 15 22 36 14 18 26 45 15 18 30 58 16 20 35 79 17 23 43 112 18 26 53 170 19 29 67 17 20 33 87 112 21 38 117 117	10	12	15	21
13 15 22 36 14 18 26 45 15 18 30 58 16 20 35 79 17 23 43 112 18 26 53 170 19 29 67 1 20 33 87 1 21 38 117 17	11	13	17	24
14 18 26 45 15 18 30 58 16 20 35 79 17 23 43 112 18 26 53 170 19 29 67	12	14	19	29
15 18 30 58 16 20 35 79 17 23 43 112 18 26 53 170 19 29 67	13	15	22	36

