5.3 Results Data Monitoring

During the trial the combined results of all schools in the trial will remain blinded to all except the statistical centre and the Independent Data Monitoring Committee (IDMC). The IDMC will review the overall quality, safety and efficacy of the data and make recommendations to the Trial Steering Committee on whether the trial protocol should be altered. If they have evidence beyond reasonable doubt that one strategy is clearly superior (or inferior) to another arm and that the result is likely to change public health practice, they should immediately report the unblinded data and their recommendation to the Trial Steering Committee.

Statistical Analysis of primary and secondary end-points

Conventional statistical analysis will be undertaken. Analysis will be undertaken for the primary objective at a per-school basis with comparisons to the population of control schools. Absent school days (both total and COVID-related) will be presented as a proportion of pupils (with binomial confidence intervals). Unadjusted transmission events will be measured as the incidence of all COVID-19 positive cases determined by both Pillar 2 and school directed testing. Transmission events will also be categorised as 'more likely' if they either have a similar genetic sequence (the cut off to be determined) or as a member of the same predefined school bubble.

Secondary analysis

The performance of DCT will be made at the level of each primary contact. The performance of the DCT will be compared to PCR using conventional exact binomial statistics. The extent of secondary transmission events will be analysed using Poisson statistics and the results

stratified according to the LFD and PCR results of the DCT-contact. The results can also be adjusted according to the day that the LFD becomes positive and the CT value of the PCR result.

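### The unadjusted form of the transmission co-primary counts all detected positives, but detection is planned to be more intense in the daily contact testing arm, so it is biased upward there even if transmission is equal

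*Protocol*

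**What the plan says.** Section 2.1 defines co-primary (ii) as an estimated number and rate of within-school transmission events. Section 3.6 (ii) names three sources of positive cases:

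- "Weekly LFD active case finding (Control and Intervention Arms")
- "Symptomatic individuals' NHS Test and Trace results obtained from Community Testing routine data (Control and Intervention Arms")
- "In-school LFD DCT testing (Interventional Arm")

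It then adds: "Positivity rates will be reported for each source separately to facilitate like-for-like comparison between arms". Epidemiological links, sequencing of a sample of links, and a review of positives found in DCT are to help decide which cases are onward transmission.

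Section 5.3 gives the unadjusted form: "Unadjusted transmission events will be measured as the incidence of all COVID-19 positive cases determined by both Pillar 2 and school directed testing". It adds a linked form: "Transmission events will also be categorised as 'more likely' if they either have a similar genetic sequence" or if they share a predefined school bubble.

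Section 3.9 expects 30% weekly-test uptake in control and, under DCT, "an increase in consent to voluntary weekly active case finding testing to 60" percent (40-60% in Table 1). It says the higher uptake will identify more positives. The Table 1 row "Initial number of outbreaks detected/school" reads 1 per month against 2 per month. Section 3.9 sets no non-inferiority margin. An independent committee is to judge whether the 95% CI for the difference in transmission events is close enough to no difference.

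Research PCR on days 2 and 7 is offered to consenting first-order contacts in both arms (sections 3.1 and 4.2) but is not among the three sources.

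**The concern.** A count of detected positives is the product of infection and detection. Here the protocol itself plans for detection to differ by arm, in two ways: a testing stream that control lacks, and higher uptake of the stream the arms share. Control contacts isolating at home enter the listed sources mainly through symptomatic testing, whereas 70% of DCT contacts are expected to be tested daily.

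Hypothesis 2 is the safety half of the trial. With no margin, the committee works from an interval alone. If detection shifts that interval, an acceptable policy can look harmful. Equally, a real excess can be dismissed as detection, because the data as pooled cannot separate the two.

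**Working it through.** **1. The plan builds in unequal detection.** Table 2 can be rebuilt by treating missed days as compound Poisson over two months:

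n per arm = (1.960 + 0.842)² × (Var_C + Var_I) / (mean_C − mean_I)²

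- Control: 2 outbreaks × 510 days. Mean 1,020; variance 2 × 510² = 520,200.
- Intervention: 2 × (u/0.30) outbreaks × (k + 3) × 10 days, where u is weekly uptake, k is the number isolating, and 3 is the index case plus two DCT positives.

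For k = 15 and u = 0.60, the mean is 4 × 180 = 720 and the variance is 4 × 180² = 129,600. So n = 7.849 × 649,800 / 300² = 56.7; Table 2 prints 58. For k = 18 and u = 0.60 the formula gives 168.8 against 170. Across all 49 cells the printed figure exceeds the formula by about 1 to 3 schools, except one cell (k = 14, u = 0.40: 14.6 against 18). Replacing 3 by 0, 1 or 2 loses the fit. The sample size therefore assumes that detected index cases rise 0.40/0.30 = 1.33 to 0.60/0.30 = 2.0 fold with uptake alone.

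**2. Inputs for the detection ratio.** From section 3.9: 50 contacts per index case, 35 in DCT and 15 isolating, and 5% of the 35 (1.75) found positive. The running text puts intervention index cases at 2 per week, but Table 1 and the 360 missed days per month (2 × 18 × 10) use 2 per month, so monthly figures are used here.

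Assumptions not in the protocol:
- 5% infected applies to all 50 contacts (2.5 infected), so DCT finds every infected tester.
- A share s of infected contacts outside DCT is found through symptoms; s = 0.2 to 0.8 is shown.

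**3. Model A: control contacts are counted only around detected index cases.**

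Ratio = (u/0.30) × (1 + 1.75 + 0.75s) / (1 + 2.5s)

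| u | s = 0.2 | s = 0.5 | s = 0.8 |
|---|---|---|---|
| 40% | 2.58 | 1.85 | 1.49 |
| 60% | 3.87 | 2.78 | 2.23 |

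**4. Model B: the same infection chains exist in control.** The extra chains revealed by higher uptake are also present in control, and their infected contacts can develop symptoms there. The denominator becomes 1 + 2.5s × (u/0.30).

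| u | s = 0.2 | s = 0.5 | s = 0.8 |
|---|---|---|---|
| 40% | 2.32 | 1.56 | 1.22 |
| 60% | 2.90 | 1.79 | 1.34 |

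Example, u = 60%, s = 0.2: 2 × 2.90 / (1 + 1.0) = 2.90.

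**5. Model C: symptomatic detection is independent of LFD uptake.** Let f be the share of infections in named contacts, L the detection probability of weekly LFD and D that of DCT.

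- Intervention: f[s + (1−s)0.7D] + (1−f)[s + (1−s)uL]
- Control: f·s + (1−f)[s + (1−s)0.30L]

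Assumed grid: s 0.1-0.6, L 0.3-0.7, D 0.5-0.9, f 0.2-0.6, u 0.4-0.6. The ratio runs from 1.06 to 3.8, with median 1.39; 61% of the grid lies below 1.5. For example, s = 0.6, L = 0.3, D = 0.5, f = 0.2, u = 0.4 gives 0.6664 / 0.6288 = 1.06.

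On similar grids, weekly LFD and symptomatic testing without DCT give 1.01 to 1.60 (median 1.07). Counting research PCR in contacts of both arms gives 1.03 to 1.93 (median 1.17).

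**6. The protocol's two safeguards.**
- By-source reporting has no control counterpart for the DCT source. For weekly LFD it gives positivity among volunteers, whose uptake is expected to differ by arm.
- The linked category draws on the same detected cases. Sharing a bubble is enough to qualify, and first-order contacts are defined as a subset of a bubble, so DCT positives in school qualify almost automatically. Infections missed in control cannot enter. The review in section 3.6 can reclassify DCT positives but cannot recover those missed infections.

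**The case against.** Five points can be made for the plan.

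- **The endpoint is not the raw count.** Co-primary (ii) is estimated in-school transmission, informed by links, sequencing and review. The pooled incidence is only its unadjusted form. This stands. A reader might infer that the pooled count is the co-primary itself, or that it supplies the committee's interval; the protocol says neither. What remains is that it names no other measure for that interval, and the linked form has the same defect.
- **The size is assumption-driven.** This stands. It is tempting to quote a 1.5- to 4-fold excess, but that is Model A alone, which gives no detection to control contacts of undetected index cases. A Poisson interval put around such a ratio would also ignore clustering by school. Table 1 labels the 2 per month as initial, and section 3.9 expects detection to fall over time.
- **Control contacts can be found without symptoms.** Sections 3.1 and 4.2 recognise asymptomatic tests outside school. This narrows the gap but does not close it.
- **School-directed testing might be read to include the research PCR.** That would shrink the bias, but section 3.6 does not list it.
- **The estimator can be left to the analysis plan, which was not available here.** This is fair for adjustment and modelling. But the protocol itself fixes the sources and the pooled definition, and those create the imbalance.

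**Conclusion.** The concern holds in a limited form. The unadjusted measure of co-primary (ii) is biased upward under DCT at equal true transmission, and the ratio exceeds 1 in every scenario computed. The direction follows from the protocol's own sources and uptake figures; the size does not. It is about 1.2 to 3.9 fold on the planning figures (Models A and B together) for an assumed symptomatic share of 20-80%. It is possibly near 1.1 if symptomatic detection dominates and is independent of LFD uptake. No single figure should be quoted as the bias. The linked category and by-source reporting do not remove it, and the protocol leaves open which measure gives the interval for hypothesis 2.

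**What to change.** In sections 3.6 (ii) and 5.3, state that the between-arm CI for hypothesis 2 comes from a measure ascertained the same way in both arms:

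- **Main measure:** symptomatic test-positive cases per school among everyone on roll, from routine Test and Trace data and regardless of consent to testing. Participants already LFD-positive who later develop symptoms must be counted the same way in both arms; otherwise a symptomatic-only count could miss DCT-arm cases found early and favour DCT. Section 4.2.1 asks DCT positives to report later symptoms, but section 4.1.2 has no such request for weekly-test positives, so that recording should be extended to them in both arms.
- **Support:** day 2 and day 7 research-PCR positivity in first-order contacts, as a proportion of contacts tested. A count would still scale with the number of index cases detected. Report completion by arm, because a missed test is not a protocol violation.
- **Supportive only:** weekly-LFD and DCT-LFD positives, by source, outside the interval given to the committee.

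The cost is mainly wording, since almost all the data are already to be collected. The price is fewer events, a wider interval, and no asymptomatic infection outside contact groups in the main comparison. The PCR proportion also has a limit: some contacts may be infected before DCT or isolation begins.

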A pragmatic cluster randomised trial in English secondary schools comparing the impact of a policy of weekly testing for COVID-19 followed by isolation of cases and their contacts, with a policy of weekly testing followed by isolation of cases and daily testing of contacts.

Study Sponsor: Department of Health and Social Care
Principal Investigator: [name]
Co-Investigators: [name], [name], [name], [name], [name]
Chief Data Analyst: [name]
Analyst: [name]

Affiliations

[name]	University of Oxford
[name]	Queen Mary University of London (NHS Test &
	Trace Public Health Lead)
[name]	University of Bristol
[name]	Department for Education
[name]	Department for Education
[name]	Public Health England
[name]	Department of Health and Social Care
[name]	Department of Health and Social Care

Document Approval

Role	Name	Signature	Date
Principle Investigator	[name]	[name]	22/02/2021
Chief Data Analyst	[name]	[name]	23/02/2021

A Note on Definitions

Throughout this protocol the following definitions are used. These are illustrated graphically in Figure 1 below

Index Case	The first known positive COVID-19 case in chain of transmission.
	This individual could be identified asymptomatically via LFD-based active case finding in the school or outside it, or via symptomatic NHS Test and Trace PCR testing
Bubble	Grouping within school created by school to limit transmission of SARS-CoV-2 within the schools. Bubbles are meant to be distinct entities with no intermixing (i.e. a member of Bubble A should have no contact with members of Bubbles B, C, D, etc.)
First-Order Contact	Close contacts of the index case.
	The subset of a bubble identified by the school as being a close contact of an index case, as defined by Government guidance:
	https://www.gov.uk/government/publications/guidance-for- contacts-of-people-with-possible-or-confirmed-coronavirus-covid- 19-infection-who-do-not-live-with-the-person/guidance-for- contacts-of-people-with-possible-or-confirmed-coronavirus-covid- 19-infection-who-do-not-live-with-the-person
	These individuals will be eligible for Daily Contact Testing or self- isolation according to national guidelines (depending on study arm and consent status)
Second-Order Contact	Close contacts of a first-order contact.
	These individuals will be identified and assessed for COVID-19 status in order to measure the secondary attack rate in each arm of the study

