3.2 Methods

3.1 Overview of Design

This is a pragmatic cluster randomised controlled study. Eligible participating schools will be stratified according to institution type, size, Free School Meal prevalence and local COVID-19 prevalence and randomly allocated into the two study arms. A schematic summarising the study design and participant sub-groups can be found in Figure 2 below.

Regular Active Case Finding. In schools participating in either arm of the study, consent will be obtained from adults/parents/guardians for voluntary weekly testing of all students and biweekly testing of all staff⁵. Tests will be performed with lateral flow devices (LFD)*, and results will be reported in the NHS Test and Trace database. LFD Tests will initially be performed as an assisted test in a school setting. Once a reliable protocol for home testing and recording of LFD is available, schools will be offered the option for at-home self-testing for weekly case finding.

Individuals who test positive will self-isolate and identify first-order contacts according to national guidelines. In addition, symptomatic cases who test positive via NHS Test and Trace, and asymptomatic cases who test positive outside the in-school testing regimen will self-isolate and report their results to the school. All individuals with a positive test will be asked to provide a PCR swab test for genomic sequencing.

1. Intervention (Daily Contact Testing) Arm

a. Public Health Intervention: Consenting first-order contacts of a COVID-positive index case will receive daily contact testing for 7 days from the point of being notified they are a close contact⁶. This will consist of a daily LFD*. Those that receive a negative LFD result can attend school for that day, but other than travelling to and from school will be instructed to continue to self-isolate outside the school setting. Those that receive a positive LFD result should not attend school and will be instructed to self-isolate for 10 days according to national guidelines. The contacts of all first-order contacts (i.e. 'second-order contacts') will be identified to allow the determination of secondary attack rate.

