3.7 Identification of Second-Order Contacts

As discussed above, the rate of COVID-19 positivity in the second-order contacts of index cases (i.e. the contacts of first-order contacts) will be an endpoint used to assess the public health effectiveness of DCT for school populations. Several methods will be used to identify the second-order contacts of index cases:

• In-school secondary contacts: As part of their existing COVID-19 management policy schools are required to segment their population into distinct 'bubbles' (e.g., year group), membership of which is unique. Members of one bubble should not be interacting with members of another. As a result, all the contacts of a member of a specific bubble should also be members of the same bubble.

In the event of a positive index case within a bubble, the school will identify those bubble members it considers to be close contacts of the index case (this will often not be the entire bubble). These close contacts (i.e. 'first-order contacts' in the context of this study) are subject to self-isolation or DCT depending on their arm.

All other members of the index case's bubble will be considered second-order contacts for the purposes of this study. Membership of each bubble will be provided by participating schools at the start of the study, and should not vary during the study.

• Household contacts of first-order contacts: Another group of second-order contacts are individuals who live in the same household as a first-order contact. These may attend the same school or may not. These individuals will be 'identified' by querying routinely collected NHS Test and Trace testing data for individuals with the same residential address as any first-order contact. The method to identify household contacts will only identify household contacts who are in Test and Trace systems.

Within the scope of this study we do not intend (for operational reasons) to identify non-school, nonhousehold contacts of first-order contacts. As first-order contacts are required to maintain selfisolation outside the school environment (even if they are undertaking DCT) this group should be minimal in size. However, it is an acknowledged limitation of the study. We also do not intend (for similar reasons) to identify individuals within the school who are not a member of the same bubble as a first-order contact but have had close contact with them. We acknowledge this as another limitation of the study.

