3.10 Governance Framework

This will be a service evaluation with the research aspect and ethical approval will be sought through Public Health England's Public Health Research Ethics framework.

The Principle Investigator and Co-principle investigators are responsible for drafting, and approval of this protocol. Review will be through the Education Evaluation Steering Group (DfE, DHSC and PHE)

and Testing Initiatives Evaluation Board (membership includes independent academics - see Appendix 5).

Overall responsibility for the study rests with the Secretary of State at the Department of Health and Social Care. The Principal Investigator has responsibility for the day-to-day delivery of the study, and for that he/she will be accountable to the Independent Trial Steering Group (TSG) (see Appendix 3 for Terms of Reference). The Study PI will be a member of this group. Test results data will be monitored by an Independent Data Monitoring Committee (IDMC) (see Section 5.2), which will report into the Trial Steering Group. Terms of Reference of the IDMC can be found in Appendix 4.

Lists of membership of study governance bodies can be found in Appendix 6.

Prior to enrollment of potential participant schools into the study advice will be sought from the local Director of Public Health, wider local authority and PHE on their willingness for the school to participate.

In the event of a suspect outbreak in a school (defined as more than 4 positive tests in a week), the local DPH and HPT will be responsible (with cooperation from the study team) for outbreak response management. Local and regional public health and teaching officials (including head teachers and school governing bodies) may raise concerns and questions with the Trial Steering Group for operational matters and the IDMC for other matters.

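### Plain Poisson analysis of secondary transmission ignores outbreak and school clustering, so its intervals are too narrow wherever cases vary more than Poisson or schools differ

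*Protocol*

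**What the plan says.** Under the secondary analysis heading of section 5.3, the protocol fixes the method: "The extent of secondary transmission events will be analysed using Poisson statistics". The results are to be "stratified according to the LFD and PCR results of the DCT-contact".

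The school appears as unit of analysis only in the preceding paragraph of 5.3: "Analysis will be undertaken for the primary objective at a per-school basis with comparisons to the population of control schools". For the secondary analyses the one unit named is the individual contact, and that is for test performance: "The performance of DCT will be made at the level of each primary contact".

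Four other places bear on the choice:

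- Section 3.1 gives the design: "This is a pragmatic cluster randomised controlled study".
- The definitions at the front say that second-order contacts are followed "in order to measure the secondary attack rate in each arm of the study".
- Section 3.7 groups them: "All other members of the index case's bubble will be considered second-order contacts for the purposes of this study". It also names positivity among second-order contacts as an endpoint for judging the public health effectiveness of daily contact testing.
- Section 3.10 provides for a "suspect outbreak in a school (defined as more than 4 positive tests in a week".

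The protocol nowhere mentions overdispersion, robust or clustered variance, a school random effect, an intracluster correlation or a design effect.

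**The concern.** A Poisson analysis takes events as independent, with variance equal to the mean. Secondary infections in this trial are unlikely to behave so. The contacts of one index case are exposed to the same source, sit in the same bubble (section 1 allows for groups of over 250 pupils) and attend the same randomised school. A few index cases may produce several secondary cases and most none, and schools may differ in how readily infection spreads.

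If so, the Poisson standard error is too small. A handful of outbreaks could then produce an apparently significant difference in secondary attack rate between arms or between LFD/PCR strata. It could also make the absence of a difference look more precisely established than it is.

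**Working it through.** **The plan's own figure.** The protocol gives no sample size, dispersion or design effect for secondary transmission. The nearest figure is Table 2 (section 3.9), for attendance. Take 15 contacts self-isolating and 60% consent over two months:

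- Control: 2 outbreaks of 51 isolating. Mean 2 × 51 = 102; variance 2 × 51² = 5202.
- Intervention: 4 outbreaks of 15 + 3 = 18. Mean 72; variance 4 × 18² = 1296.
- Schools per arm = (1.96 + 0.84)² × (5202 + 1296) / (102 − 72)² ≈ 57. A two-sample t calculation gives 58, the table's value.

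The same t calculation comes within two schools of all 49 legible cells. The attendance calculation therefore treats events as batches arriving at schools, with the school as unit. The Poisson sentence in 5.3 carries no such allowance. Table 2 shows the authors' model but says nothing about the dispersion of infections: the 51 isolate by rule.

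**Effect of extra variation.** Let φ be the variance-to-mean ratio. The correct standard error is √φ times the Poisson one, and a nominal 95% interval covers 2Φ(1.96/√φ) − 1. The values of φ are assumed. If cases per index case are negative binomial with mean m and dispersion k, then φ = 1 + m/k; with m = 0.5, k = 1, 0.5 and 0.2 give φ = 1.5, 2.0 and 3.5.

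| φ (assumed) | SE too small by a factor of | Coverage | False-positive rate |
|---|---|---|---|
| 1.0 | 1.00 | 95.0% | 5.0% |
| 1.5 | 1.22 | 89.0% | 11.0% |
| 2.0 | 1.41 | 83.4% | 16.6% |
| 3.5 | 1.87 | 70.5% | 29.5% |

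**A second route.** With 50 contacts per cluster and an assumed intracluster correlation of 0.005 to 0.05, the design effect 1 + 49 × ICC is 1.25 to 3.45. The false-positive rate is 7.9% to 29.1%.

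**Simulation under no true difference.** There were 50 schools per arm and on average 2 outbreaks per school. That is 50 × 1 per month × 2 months = 100 index cases per arm, as section 3.9 expects for control schools. The test was at nominal 5%.

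- Plain Poisson on school counts, Poisson cases per outbreak: 10.7% (mean 0.5), 16.2% (mean 1) and 24.9% (mean 2). The mean of 2 borrows section 3.9's figure for positive contacts found by daily testing, as a stand-in.
- Plain Poisson with outbreaks as exposure, Poisson cases with one common mean: 4.9% to 5.0%. This is the benign case.
- The same with negative binomial cases, k = 1: 10.5% (mean 0.5) and 25.8% (mean 2).
- A t-test on school totals: 4.6% to 5.0% in all these settings.

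**The case against.** Section 5.3 is a short summary, and Poisson statistics is a loose label. A Poisson model with scaled or clustered standard errors would fit it, and a statistical analysis plan that is not at hand may say so. That stands as a caution. Yet the protocol names a method, gives the per-school basis to the primary objective alone, and says nothing elsewhere that supplies the allowance. Read as written, it is plain Poisson.

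The dispersion is also assumed throughout. This stands. The outbreak threshold in 3.10 counts all positive tests in a school and is a governance trigger, so it is no measure of dispersion. In the benign case there is no inflation. That case, however, requires equal transmissibility across index cases, bubbles and schools, which nothing in the protocol supports.

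The sentence specifies strata by the contact's LFD and PCR results, and LFD results during contact testing exist only in intervention schools. A school effect common to both strata may partly cancel there, so school clustering need not inflate that contrast as it would a comparison of arms. Variation between individual contacts would not cancel. The between-arm use rests on the front definitions and 3.7, since 5.3 does not spell out a Poisson test of the arms.

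A reader might infer that the committee's safety judgement rests on these intervals. It does not: section 3.9 ties that judgement to the difference between arms in transmission events, a co-primary endpoint, and 5.3 puts the primary objective on a per-school basis.

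**Conclusion.** The point holds as a conditional one. The method stated in 5.3 does not match the cluster design or the bubble-based definition of second-order contacts. It understates uncertainty whenever cases per index case vary more than Poisson or transmission differs between schools. For an assumed variance-to-mean ratio of 1.5 to 3.5, a nominal 95% interval covers about 89% to 71%; at a ratio of 1 nothing is lost. The direction follows from the design, whereas the size is an assumption that the protocol cannot settle.

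The reach is limited to the secondary attack rate comparison between arms and, less certainly, the LFD/PCR strata. The powered attendance endpoint and the co-primary transmission interval are untouched. The change is worth making because secondary attack rate is an effectiveness endpoint and the correction is nearly free.

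**What to change.** In the secondary analysis text of 5.3, replace Poisson statistics with a negative binomial or quasi-Poisson model for secondary transmission events, with second-order contacts at risk as offset and standard errors clustered on school. For the between-arm contrast, school-level rates compared by a permutation test are an acceptable alternative. If the statistical analysis plan already specifies this, bring 5.3 into line with it.

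The offset can come from the bubble lists that schools supply. For household contacts it covers only those found in Test and Trace systems, a limit that 3.7 already states. The cost is a sentence in 5.3 and its counterpart in the analysis plan; standard software suffices and no new data are needed. The downside is wider intervals: by a factor of about 1.2 to 1.9 over the assumed range, and hardly any if the data prove to be Poisson.
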